
Secondary for Part A
 
 To evaluate the efficacy of baricitinib in children with JIA-U or ANA-positive uveitis in the most severely affected eye and less affected eye To evaluate the efficacy of adalimumab in children with JIA-U or ANA-positive uveitis in the most severely affected eye and less affected eye 	
 Change in SUN grade of cells in the anterior chamber through Week 24 in the most severely affected eye. Change in SUN grade of cells in the anterior chamber through Week 24 in the less severely affected eye (if applicable). In patients with bilateral uveitis disease at baseline: Proportion of responders at Week 24, defined according to the SUN criteria as a 2-step decrease in the level of anterior chamber cells in the most severely affected eye at baseline (or both eyes if the inflammation grade is the same in both eyes) and a 1-step decrease in the level of anterior chamber cells in the less severely affected eye at baseline^a. Change in visual acuity measured by age-appropriate LogMAR test through Week 24. Change in vitreous haze through Week 24 in each affected eye. Change in grade of flare in the anterior chamber through Week 24 in each affected eye. Change in overall uveitis-related disability: 
 Change in Patient Uveitis-related Disease Activity through Week 24. Change in Patient Uveitis-related Improvement at Week 12 and Week 24. Change in Patient Arthritis Disease Activity through Week 24. Change in Patient Arthritis Improvement at Week 12 and Week 24. Change in Ophthalmologist Uveitis-related Disease Activity through Week 24.

Objectives	Endpoints
	
 ○ Change in Ophthalmologist Uveitis-related Improvement at Week 12 and Week 24. ● Proportion of patients with inactive anterior uveitis (using SUN definition) in each affected eye through Week 24. ● Time to inactive anterior uveitis disease (using SUN definition) in each affected eye. ● Proportion of patients who are able to taper concomitant topical corticosteroids to <2 drops per day and to 0 drops per day. ● PediACR30/50/70/90/100 response rates (for patients with JIA-U).

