Abbreviations: AE = adverse event; ANA = antinuclear antibody; JIA = juvenile idiopathic arthritis; LogMAR = logarithm of the minimum angle of resolution; OLE = open-label extension; PediACR = Pediatric American College of Rheumatology; PK = pharmacokinetic(s); SUN = Standardization of Uveitis Nomenclature.

a Response is defined according to the SUN criteria as a 2-step decrease in the level of inflammation (anterior chamber cells) or decrease to 0 through Week 24 in the eye most severely affected at baseline.

5. Study Design

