9.1.2. Secondary Efficacy Assessments

Secondary endpoints (assessed at each visit) are as follows:

- Change in SUN grade of cells in the anterior chamber through Week 24 (Part A) and through Week 284 (Part B) in the most severely affected eye.
- Change in SUN grade of cells in the anterior chamber through Week 24 and Week 284 in the less severely affected eye (if applicable).
- In patients with bilateral uveitis disease at baseline: proportion of responders at Weeks 24 and 284, defined according to the SUN criteria as a 2-step decrease in the level of anterior chamber cells in the most severely affected eye at baseline (or both eyes if the inflammation grade is the same in both eyes) and a 1-step decrease in the level of anterior chamber cells in the less severely affected eye at baseline.
- Change in visual acuity measured by age-appropriate LogMAR test through Week 24.

- Change in vitreous haze through Week 24 in each affected eye.
- Change in grade of flare in the anterior chamber through Week 24 and Week 284 in each affected eye.
- Change in overall uveitis-related disability:
 - Change in Patient Uveitis-related Disease Activity through Week 24.
 - Change in Patient Uveitis-related Improvement at Week 12 and Week 24.
 - Change in Patient Arthritis Disease Activity through Week 24.
 - Change in Patient Arthritis Improvement at Week 12 and Week 24.
 - Change in Ophthalmologist Uveitis-related Disease Activity through Week 24.
 - Change in Ophthalmologist Uveitis-related Improvement at Week 12 and Week 24.
- Proportion of patients with inactive anterior uveitis (using SUN definition) in each affected eye through Week 24 and Week 284.
- Time to inactive anterior uveitis disease (using SUN definition) in each affected eye.
- Proportion of patients who are able to taper concomitant corticosteroids.
- Time to treatment response: response is defined by a 2-step decrease in the level of inflammation (anterior chamber cells) or decrease to zero in the eye most severely affected at baseline.
- Proportion of responders at Week 284.
- Pediatric American College of Rheumatology (PediACR) 30/50/70/90/100 response rates (for patients with JIA-U).
- Safety variables:
 - AEs, including SAEs
 - Permanent discontinuation of investigational product due to AE, and
 - Temporary interruption of investigational product.

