9.1.2.2. Uveitis Disease Activity

The definition of uveitis disease activity used in this study is based on the SUN Working Group criteria (Table JAHW.11; Jabs et al. 2005). Inactive disease is defined as the presence of 0 anterior chamber cells upon slit-lamp examination.

Table JAHW.11. Uveitis Disease Activity Terminology

Term	Definition
Inactive	Grade 0 cells ^a
Worsening activity	2-step increase in level of inflammation (e.g., anterior chamber cells, vitreous haze) or increase from grade 3+ to 4+
Improved activity	2-step decrease in level of inflammation (e.g., anterior chamber cells, vitreous haze) or decrease to grade 0
Remission	Inactive disease for ≥ 3 months

^a Applies to anterior chamber inflammation.

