10.3.3.2. Secondary Analyses

Secondary efficacy and health outcomes analyses (Table JAHW.12) will be based on all participants who take at least 1 age-based dose of investigational product for Part A. Baseline is defined as Week 0.

The secondary efficacy and health outcomes analysis for Part B will be addressed in the SAP.

Table JAHW.12. Secondary Efficacy Endpoint Analyses for Part A

Measure	Endpoint	Analysis Method
SUN grade of cells in the anterior chamber in the most severely affected eye	Change from baseline	Summary statistics
SUN grade of cells in the anterior chamber in the less severely affected eye (if applicable)	Change from baseline	Summary statistics
In patients with bilateral uveitis disease at baseline: Responders, defined according to the SUN criteria as a 2-step decrease in the level of anterior chamber cells in the most severely affected eye at baseline (or both eyes if the inflammation grade is the same in both eyes) and a 1-step decrease in the level of anterior chamber cells in the less severely affected eye at baseline.	Proportion of patients	Summary statistics
Visual acuity by age-appropriate LogMAR test in each eye	Change from baseline	Summary statistics
Vitreous haze in each affected eye	Change from baseline	Summary statistics
Grade of flare in the anterior chamber in each affected eye	Change from baseline	Summary statistics
Overall uveitis-related disability: 
 ○ Change in Patient Uveitis-related Disease Activity through Week 24. ○ Change in Patient Uveitis-related Improvement at Week 12 and Week 24. ○ Change in Patient Arthritis Disease Activity through Week 24. ○ Change in Patient Arthritis Improvement at Week 12 and Week 24. ○ Change in Ophthalmologist Uveitis-related Disease Activity through Week 24. ○ Change in Ophthalmologist Uveitis-related Improvement at Week 12 and Week 24. 	Change from baseline	Shift table
Proportion of patients with inactive anterior uveitis disease status in each affected eye	Proportion of affected eyes	Summary statistics
	Time to inactive disease status	Summary statistics

Measure	Endpoint	Analysis Method
Concomitant topical corticosteroid tapering status, for patients eligible for corticosteroid tapering	Proportion of patients	Summary statistics
PediACR 30/50/70/90/100	Proportion of responders	Summary statistics

Abbreviations: PediACR = Pediatric American College of Rheumatology; SUN = Standardization of Uveitis Nomenclature.

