Appendix 10. Protocol Amendment History

The Protocol Amendment Summary of Changes Table for the current amendment is located directly before the Table of Contents (TOC).

Amendment [d]: 07-Nov-2020

Overall Rationale for the Amendment

The overall changes and rationale for the changes made to this protocol are described in the following table. Editorial revisions with no impact on protocol design or implementation were also made. These revisions are not noted in this protocol amendment summary except where contained in a section with substantive changes.

Amendment Summary for Protocol I4V-MC-JAHW Amendment (d)

Section # and Name	Description of Change	Brief Rationale
Section 1. Synopsis Section 4. Objectives and Endpoints	Addition of footnote for endpoints in Secondary Part A	Clarification of response definition for Secondary Endpoints related to bilateral uveitis disease SUN criteria.
Section 2. Schedule of Activities Appendix 9. Provisions for Changes in Study Conduct During Exceptional Circumstances	Addition of provisional language for participation in the study during exceptional circumstances such as the COVID-19 pandemic	This language and appendix describe the types of changes to study conduct that will be possible during exceptional circumstances. These changes to study conduct will only be implemented with approval from the sponsor and if permitted by local regulations.
Section 2. Schedule of Activities Section 9.4.6.3. Tanner Stage Scale Section 11. References	Addition of baseline Tanner Staging Scale	Baseline assessment of sexual maturity (Tanner Staging) was included based on feedback from regulatory agencies.
Section 2. Schedule of Activities	Addition of x-ray procedure	Imaging procedures were included or increased in frequency based on feedback from regulatory agencies for additional monitoring of bone growth and assessment of symptomatic areas of bones/joints.
	Height measurements were added for all study visits	The additional measurements for height were added for additional growth monitoring.
	
 • Height schedule changed to Initial Protocol design • Added Weight in V1 Screening • Adjusted footnote f in Table JAHW.1. to include imaging requirements and specify ± timing for 	
 • Error in previous amendment. • For Clarity. 
*Only applicable if Amendment (c) is in effect. These changes are not present in Amendment (b).

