SUN grade	SUN grade of cells in the anterior chamber	
 ▪ SUN grade of cells in the anterior chamber in the most severely affected eye ▪ SUN grade of cells in the anterior chamber in the less severely affected eye (if applicable) ▪ In patients with bilateral uveitis disease at baseline: Proportion of responders, defined according to the SUN criteria as a 2-step decrease in the level of anterior chamber cells in the most severely affected eye at baseline (or both eyes if the inflammation grade is the same in both eyes) and a 1-step decrease in the level of anterior chamber cells in the less severely affected eye at baseline. 	
Change from baseline: observed SUN grade – baseline SUN grade
 
Change from baseline: observed SUN grade – baseline SUN grade ≤ -2 in most severely affected eye at baseline (or both eyes if the inflammation grade is the same in both eyes) and ≤ -1 in the less severely affected eye at baseline
	
Missing if baseline or observed value is missing.
 
Missing if baseline or observed value is missing or if the patient does not have bilateral uveitis disease at baseline.

LogMar test	Visual acuity is measured by age-appropriate LogMar test in each eye	
 ▪ LogMAR test score 	Change from baseline: observed LogMAR test score – baseline LogMAR test score	Missing if baseline or observed value is missing.
Vitreous haze	Slit-lamp examination is used for assessment of vitreous haze	
 ▪ Vitreous haze in each affected eye 	Change from baseline: observed vitreous haze – baseline vitreous haze	Missing if baseline or observed value is missing.
Grade of flare	Flare will be assessed using a slit-lamp, and graded using the SUN grading scheme	
 ▪ Grade of flare in the anterior chamber in each affected eye 	Change from baseline: observed grade of flare – baseline grade of flare	Missing if baseline or observed value is missing.

Measure	Description	Variable	Derivation / Comment	Definition of Missing
Inactive anterior uveitis disease status	Inactive anterior uveitis disease status is ascertained using the SUN criteria.	▪ Proportion of eyes with inactive anterior uveitis	Proportion of eyes with inactive anterior uveitis is calculated by the number of eyes that achieve inactive disease status divided by the total number of affected eyes.	Missing if disease activity is missing

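### SAP Table JAHW.7.1 leaves the grade-0 alternative out of the Part A bilateral responder; with SUN grades subtracted at face value, a child with both eyes at 1+ who clears fully cannot respond

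*SAP*

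**What the plan says.** The bilateral responder row of SAP Table JAHW.7.1 (Section 7.1) requires "observed SUN grade – baseline SUN grade ≤ -2 in most severely affected eye at baseline", applied to both eyes when their grades are equal, "and ≤ -1 in the less severely affected eye at baseline". It gives no alternative for an eye that reaches grade 0. SAP Table JAHW.7.2 assigns nonresponder imputation to this endpoint, and under SAP Section 6.3.1.1 a patient who does not meet the criterion is a nonresponder.

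Protocol Table JAHW.5 (Section 4), like the synopsis, lists the Part A endpoint with a footnote marker: "a 1-step decrease in the level of anterior chamber cells in the less severely affected eye at baseline^a". Footnote a defines response as a 2-step decrease "or decrease to 0 through Week 24 in the eye most severely affected at baseline". The amendment history gives the reason for adding it under Amendment (d): "Clarification of response definition for Secondary Endpoints related to bilateral uveitis disease SUN criteria". The footnote is current text.

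The protocol is not uniform. Section 9.1.2 gives the endpoint without the footnote ("proportion of responders at Weeks 24 and 284, defined according to the SUN criteria as a 2-step decrease"), and so does Table JAHW.12 ("In patients with bilateral uveitis disease at baseline: Responders, defined according to the SUN criteria as a 2-step decrease"). SAP Tables JAHW.4.2 and JAHW.7.2 follow that shorter form. For the primary endpoint, SAP Section 7.1 keeps the decrease-to-zero alternative. Neither document defines bilateral disease at baseline or gives a step a numerical meaning.

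**The concern.** The SUN cell scale in protocol Table JAHW.9 runs 0, 0.5+, 1+, 2+, 3+, 4+, and inclusion criterion 3 admits patients from grade 1+. An eye that starts at 1+ has only one unit to lose at face value, so a threshold of -2 is out of its reach. The grade-0 alternative exists for this case, and it is missing from the row that programmers will implement.

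At stake is a listed secondary efficacy proportion in both arms. A child whose two 1+ eyes both clear would appear in one report as a primary responder, as two inactive eyes, and as a bilateral nonresponder. Dropping an alternative route to response can only lower the count. At the planned minimum arm sizes the bilateral subset is at most 20 (baricitinib) or 4 (adalimumab), so one misclassified child would move the proportion by at least 1/20 = 5 or 1/4 = 25 percentage points.

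**Working it through.** The plan gives no figure to reproduce; the check applies the derivation rule to every grade combination.

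**Inputs**
- Scale: 0, 0.5+, 1+, 2+, 3+, 4+ (protocol Table JAHW.9).
- Worse eye at baseline: 1+ to 4+ (protocol Section 6.1, criterion 3).
- Rule: worse eye (both eyes if equal) changes by ≤ -2, and a less affected fellow eye changes by ≤ -1 (SAP Table JAHW.7.1).
- Grade-0 alternative: from protocol footnote a, applied to the worse eye, or to both eyes when tied.

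**The key case, both eyes 1+ clearing to 0**
- Face-value subtraction: 0 - 1 = -1 in each eye. -1 is not ≤ -2, so the child is a nonresponder. No better outcome exists, so response is impossible.
- Face-value subtraction with the alternative: both eyes reach 0, so the child is a responder.
- Rank coding (0, 0.5+, 1+, … coded 0, 1, 2, …): 0 - 2 = -2 in each eye, so the child is a responder with or without the alternative.

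**All combinations.** Every baseline pair (fellow eye no worse than the worse eye) was crossed with all 6 × 6 = 36 Week 24 pairs, and the combinations scored as response were counted.

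| Coding and rule | Both eyes ≥1+ (10 baseline pairs) | Fellow eye 0.5+ also allowed (14 pairs) |
|---|---|---|
| Face value, as in the SAP | 71 | 71 |
| Face value, grade-0 alternative added | 72 | 72 |
| Face value, alternative not extended to tied eyes | 71 | 71 |
| Rank, with or without the alternative | 85 | 95 |

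The one combination that the alternative adds is 1+/1+ to 0/0.

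**Full clearing of both eyes scored as non-response**
- Face value, as in the SAP: 1 of 10 pairs (1+/1+), or 5 of 14 if a 0.5+ fellow eye counts as bilateral disease.
- Face value with the alternative: 0 of 10, or 4 of 14. The four have a fellow eye at 0.5+ (worse eye 1+, 2+, 3+ or 4+). They fail the -1 rule because 0 - 0.5 = -0.5, which footnote a does not address.
- Rank coding: none.

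**Effect of the coding itself.** With the alternative in place, 85 - 72 = 13 combinations with both eyes ≥1+ still depend on the coding. For example, a worse eye going from 2+ to 0.5+ changes by -1.5 at face value but by two ranks.

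**The case against.** The strongest reply is that the harm needs two readings at once: the SAP row read as label subtraction, and footnote a extended to tied eyes although it names only the worse eye. If the footnote is confined to its words, adding it changes nothing (71 either way). If steps are counted, it also changes nothing (85 either way). The Variable column of the same row does speak of 2-step and 1-step decreases, and on counts alone the undefined step matters more (13 combinations) than the missing alternative (1).

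Part of this stands. The tied-eye extension is an inference and the coding is not certain, so the consequence is conditional. Two things support it. First, the derivation is written as a subtraction of grades, the same cell uses the same subtraction for change in SUN grade, and no rank coding appears in the SAP. Second, the endpoint applies the worse-eye rule to both eyes when they are tied, and protocol Table JAHW.11 defines SUN improvement as a "2-step decrease in level of inflammation (e.g., anterior chamber cells, vitreous haze) or decrease to grade 0" without limiting it to one eye. With both eyes at 1+ or worse and face-value subtraction, the footnote would have no effect at all unless it covered tied eyes.

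It is also true that the SAP wording matches protocol Section 9.1.2 and Table JAHW.12, so part of the inconsistency is inherited. That widens the correction but does not remove it. The protocol's Part B bilateral endpoint carries no footnote, so limiting the change to Week 24 follows the documents. Finally, combination counts are not patient frequencies, and the number of children affected could be zero.

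**Conclusion.** The concern holds. The omission is a plain mismatch between SAP Table JAHW.7.1 and protocol footnote a. Its consequence rests on two assumptions: face-value subtraction, which is the literal reading of the row, and application of the footnote to both tied eyes, which is a well-supported inference. Under both, exactly one baseline pair (1+/1+) is misclassified on full clearing, always towards non-response. Under rank coding nothing is misclassified, so the result turns on a choice the SAP does not state. The affected endpoint is a descriptive Part A secondary proportion; the primary analysis and the stopping and success rules are untouched. It should be corrected before programming.

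**What to change.** 1. In the bilateral responder row of SAP Table JAHW.7.1, add a decrease to grade 0 as an alternative to the -2 criterion in the worse eye, and in both eyes when baseline grades are equal. Full clearing from 1+/1+ is then a response under either coding.
2. State for this row whether -2 and -1 are differences between grade labels or steps on the Table JAHW.9 scale.
3. Define bilateral uveitis at baseline, in particular whether a fellow eye at 0.5+ counts.
4. Carry footnote a into SAP Tables JAHW.4.2 and JAHW.7.2, and align protocol Section 9.1.2 (for Week 24) and Table JAHW.12.
5. Leave the primary endpoint definition as it is.

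The cost is SAP wording, programming of one row and alignment of two places in the protocol. No new data are needed.

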that the baricitinib treatment response is greater than 57%, otherwise the study will be considered negative.

Efficacy and health outcome endpoints will be summarized using descriptive statistics. The last-observation-carried-forward approach will be used to impute missing data.

Categorical data will be summarized as frequency counts and percentages. The proportions and 95% confidence interval will be reported. Missing data will be imputed using the modified nonresponder imputation method.

Two interim analyses will be performed to determine if the study should be stopped for futility when 10 and 20 baricitinib-treated patients have completed 24 weeks of treatment. At each interim analysis, the posterior probability of the treatment response rate being lower than 40% will be calculated, and the study will be stopped if this probability is greater than 75% (otherwise the study will continue).

Descriptive response rates will be evaluated in adalimumab-treated patients.

An analysis will evaluate response rates in MTX-IR adalimumab-treated patients and MTX-IR baricitinib-treated patients.

All safety data will be descriptively summarized using corresponding populations.

Ethical Considerations of Benefit/Risk

Based on the efficacy of baricitinib demonstrated in the Phase 3 RA program and the observed safety profile, the probability of a positive benefit/risk warrants this study to be conducted, given the unmet need in patients with JIA-U and ANA-positive uveitis.

2. Schedule of Activities

The Schedule of Activities described below should be followed for all participants enrolled in Study JAHW. In the event participation in this study is affected by exceptional circumstances (such as pandemics or natural disasters), please refer to Appendix 9 and consult with the sponsor's representative for additional guidance.

Table JAHW.1. Schedule of Activities

Visit #	Screening		Treatment Period Part A							Early Termination	Post-Treatment Follow-Up						
	V1	V1a	V2 ^a Baseline	V3	V4	V5	V6	V7	V8								
Study Week			W0	W4	W8	W12	W16	W20	W2 4	Any Week							
Study Day (Approximately)	-42 to -1		0	28	56	84	112	140	168	Any Day							28 ± 5 Days after Last Dose
Visit Window (Days)				±4													
Informed consent and assent ^d	X																
Complete medical history	X																
Immunization record	X		X	X	X	X	X	X	X								
Demographics	X																
Physical examination ^e	X																
Tanner Stage Scale ^z			X														

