6.1. General Considerations

This plan describes *a priori* statistical analyses for efficacy, health outcomes, and safety that will be performed.

Statistical analysis of this study will be the responsibility of Eli Lilly and Company (Lilly). The statistical analyses will be performed using SAS® Version 9.4 or a more recent version.

Not all displays described in this SAP will necessarily be included in the clinical study report (CSR). Not all displays will necessarily be created as a “static” display. Some may be incorporated into interactive display tools instead of or in addition to a static display. Any display described in this SAP and not included in the CSR would be available upon request.

Bayesian analysis will be used as the primary analysis method for the primary endpoint and interim analysis. The posterior probability will be reported and the conclusion will be made based on the prespecified success criteria. The primary endpoint is the proportion of patients with response at Week 24. Response is defined as a 2-step decrease in the level of inflammation (anterior chamber cells) or decrease to 0 in the eye most severely affected at baseline, measured by the SUN criteria (Jabs et al. 2005). **CCI**

Unless otherwise specified, for the endpoints that may relate to both eyes, such as patients with uveitis affecting both eyes, the summary of the data for a given endpoint measure will be based on both affected eyes. The summary statistics may be grouped into “less severely affected eye” and “more severely affected eye” or “right eye” and “left eye” subgroups. The “less severely affected eye” and “more severely affected eye” are defined by the baseline SUN grade for each patient with a higher SUN grade indicating more severity.

Efficacy and health outcomes endpoints will also be summarized using descriptive statistics for the baricitinib arm and adalimumab arm. No treatment comparison will be conducted.

Continuous data will be summarized in terms of the mean, standard deviation (SD), minimum, maximum, and median. Categorical data will be summarized as frequency counts and percentages.

All safety data will be descriptively summarized.

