SUN grade of cells in the anterior chamber in the most severely affected eye	Change from baseline	Summary statistics	LOCF
SUN grade of cells in the anterior chamber in the less severely affected eye (if applicable)	Change from baseline	Summary statistics	LOCF
In patients with bilateral uveitis disease at baseline: Responders, defined according to the SUN criteria as a 2-step decrease in the level of anterior chamber cells in the most severely affected eye at baseline (or both eyes if the inflammation grade is the same in both eyes) and a 1-step decrease in the level of anterior chamber cells in the less severely affected eye at baseline.	Proportion of patients	Summary statistics	NRI
Visual acuity by age-appropriate LogMAR test in each eye	Change from baseline	Summary statistics	LOCF
Vitreous haze in each affected eye	Change from baseline	Summary statistics	LOCF
Grade of flare in the anterior chamber in each affected eye	Change from baseline	Summary statistics	LOCF
Overall uveitis-related disability: Change in Patient Uveitis-related Disease Activity through Week 24. Change in Patient Uveitis-related Improvement at Week 12 and Week 24. Change in Patient Arthritis Disease Activity through Week 24. Change in Patient Arthritis Improvement at Week 12 and Week 24. Change in Ophthalmologist Uveitis-related Disease Activity through Week 24. Change in Ophthalmologist Uveitis-related Improvement at Week 12 and Week 24.	Change from baseline	Summary statistics	LOCF
Proportion of number of eyes with inactive anterior uveitis disease status in each affected eye	Proportion of affected eyes	Summary statistics	NRI

Measure	Endpoint	Analysis Method	Handling of Missing Data
	Time to inactive disease status	Time-to flare will be summarized graphically by treatment group using Kaplan-Meier estimates.	censoring
Concomitant topical corticosteroid tapering status, for patients eligible for corticosteroid tapering	Proportion of patients	Summary statistics	NRI
PediACR 30/50/70/90/100	Proportion of responders	Summary statistics	NRI

Abbreviations: LOCF = last observation carried forward; LogMAR = logarithm of the minimum angle of resolution; NRI = nonresponder imputation; PediACR = Pediatric American College of Rheumatology; SUN = Standardization of Uveitis Nomenclature.

Table JAHW.7.3. Description and Derivation of Health Outcomes and Quality-of-Life Measures for Part A

Measure	Description	Variable	Derivation / Comment	Definition of Missing

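### Inactive uveitis is stated as a proportion of patients but computed as a proportion of eyes, so children with bilateral disease count twice and the missing-data rule does not fit the denominator

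*SAP*

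**What the plan says.** **Stated endpoint.** Protocol Section 4 (Table JAHW.5) gives "Proportion of patients with inactive anterior uveitis (using SUN definition) in each affected eye through Week 24". The protocol synopsis and SAP Table JAHW.4.2 carry the same endpoint. Protocol Sections 9.1.2 and 10.3.6.1 (age subgroups) also count patients.

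**Computed quantity.** SAP Table JAHW.7.1 derives the "number of eyes that achieve inactive disease status divided by the total number of affected eyes". SAP Table JAHW.7.2 names the measure "Proportion of number of eyes with inactive anterior uveitis disease status in each affected eye". Protocol Table JAHW.12 words the measure per patient but gives the endpoint in the same row as "Proportion of affected eyes".

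**Two-eye rule.** SAP Section 6.1 says that "the summary of the data for a given endpoint measure will be based on both affected eyes". It then permits, but does not require, grouping by more and less severely affected eye or by right and left eye. Protocol Section 10.3.1 does the same.

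**Missing data.** SAP Table JAHW.7.2 assigns nonresponder imputation (NRI). SAP Section 6.3.1.1 defines NRI for patients: a patient is a nonresponder if the response criteria are not met or the visit is entirely missing.

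**Intervals.** The protocol synopsis says of categorical data that "The proportions and 95% confidence interval will be reported". SAP Section 6.1 says only that "Categorical data will be summarized as frequency counts and percentages", and the method given for this endpoint is summary statistics.

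**Time to inactive disease.** SAP Table JAHW.7.1 derives it for each affected eye. The method cell in Table JAHW.7.2 reads "Time-to flare will be summarized graphically by treatment group using Kaplan-Meier estimates", which names flare rather than inactive disease and gives no rule for a child's two eyes.

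**The concern.** A proportion of patients and a proportion of eyes are different quantities whenever some patients contribute two eyes. Protocol Section 3.2 describes bilateral disease as typical in ANA-positive JIA patients with uveitis, so this will arise often. Three things follow.

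- The reported figure does not answer the stated endpoint. A reader of the objectives cannot tell whether a result means eyes, patients with every affected eye inactive, or patients with at least one inactive eye.
- Bilateral patients get double weight. This shifts the pooled rate if response differs between unilateral and bilateral disease.
- Two eyes of one child on one systemic drug are unlikely to be independent, so an interval that treats pooled eyes as independent would overstate precision. This third point depends on an interval being calculated that way.

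**Working it through.** **1. The plan's own figures.** No precision is stated for this endpoint. The nearest design figure is for the primary endpoint (protocol Section 10.1). With a Beta(1,1) prior and 20 responders of 30, P(θ > 0.57) = 0.848; with 19 of 30 it is 0.745. The stated value of above 80% reproduces. It is a patient-level calculation and does not depend on the point raised here.

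**2. Inputs.** N = 20 patients is the updated baricitinib minimum (protocol Section 5.2). The bilateral share *b* and the within-patient correlation ρ are not in the documents. I take *b* = 50%, 70% and 100%, and ρ = 0 to 0.9. The eye-level rate p = 0.5 is also an assumption.

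**3. Weighting.** With *b* = 70%, 14 patients have two affected eyes and 6 have one: 28 + 6 = 34 eyes. Bilateral patients supply 28/34 = 82% of the eye denominator but 14/20 = 70% of the patients.

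**4. Effect of the unit on the estimate.** For a bilateral patient, P(both eyes inactive) = p² + ρp(1−p) and P(at least one inactive) = 2p − P(both). Take p = 0.5 in all eyes, 14 of 20 bilateral.

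| Quantity | ρ = 0.3 | ρ = 0.9 |
|---|---|---|
| Inactive eyes / affected eyes | 50% | 50% |
| Patients with all affected eyes inactive | (6×0.5 + 14×0.325)/20 = 37.8% | (6×0.5 + 14×0.475)/20 = 48.3% |
| Patients with any affected eye inactive | (6×0.5 + 14×0.675)/20 = 62.3% | (6×0.5 + 14×0.525)/20 = 51.8% |

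**5. Effect on an interval, if one is put on pooled eyes.** Number of eyes m = N(1+b). Design effect = 1 + 2Nbρ/m = 1 + 2bρ/(1+b). The correct standard error is the naive one times the square root of the design effect.

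- *b* = 50%, ρ = 0.3: design effect 1 + 0.3/1.5 = 1.20, ratio 1.10.
- *b* = 70%, ρ = 0.5: design effect 1 + 0.7/1.7 = 1.41, ratio 1.19.
- *b* = 100%, ρ = 0.9: design effect 1 + 1.8/2 = 1.90, ratio 1.38.
- ρ = 0: ratio 1.00 for any *b*.

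At *b* = 70% the naive Wald half-width is 1.96 × √(0.25/34) = 16.8 points. The corrected half-width is 18.8 (ρ = 0.3), 20.0 (0.5), 21.1 (0.7) or 22.2 (0.9). One row per patient gives 1.96 × √(0.25/20) = 21.9.

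An exact (Clopper-Pearson) interval is conservative and absorbs part of this. I calculated its coverage on pooled eyes for N = 20, averaged over true rates of 20% to 80%.

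| Bilateral share | ρ = 0 | ρ = 0.3 | ρ = 0.5 | ρ = 0.7 | ρ = 0.9 |
|---|---|---|---|---|---|
| 50% | 96.9% | 95.1% | 93.8% | 92.4% | 91.1% |
| 70% | 96.8% | 94.4% | 92.7% | 91.0% | 89.2% |
| 100% | 96.6% | 93.7% | 91.6% | 89.5% | 87.5% |

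**6. Missing data.** The NRI rule classifies a patient; Table JAHW.7.1 counts eyes. If a bilateral child misses Week 24, the rule does not say whether one or two failures enter the eye denominator. If one eye is graded and the other is not, the visit is not entirely missing, and the rule gives no instruction for the ungraded eye.

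**The case against.** The strongest reply has four parts.

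- **The objective is itself eye-specific.** The phrase about each affected eye can be read as asking for eye-level results, and protocol Table JAHW.12 already lists affected eyes. This is fair, and it rules out one inference a reader might draw: that the SAP departed from a clear protocol. The protocol carries both units, so the conflict lies within and across both documents. It still needs settling, because the stated denominator is patients in every place where the endpoint is defined.
- **The documents already allow grouping by eye.** Rows for the more and less severely affected eye would count each patient once per row. That stands as a route to a fix. As written the grouping is optional, while Table JAHW.7.1 fixes a pooled formula.
- **No interval is specified.** A reader might infer that the plan promises 95% intervals for this endpoint and that they will be too narrow. The documents do not establish that. The interval appears in one general synopsis sentence, and the next sentence refers to modified nonresponder imputation, which protocol Section 10.3.1 restricts to primary efficacy data. No interval method is given, and the SAP sets no interval for this endpoint. Likewise, pooling of both eyes in one Kaplan-Meier curve is an inference: the tables say neither that eyes are pooled nor that they are kept apart.
- **The endpoint is descriptive.** There is no test and no treatment comparison, and the double weight moves the pooled rate only if response differs by laterality. Both statements are correct. They limit the consequence but do not resolve which quantity is reported.

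**Conclusion.** The unit conflict holds. Followed as written, the plan reports inactive eyes over affected eyes where the objectives name a proportion of patients, counts each bilateral child twice, and applies a patient-level imputation rule to an eye-level denominator.

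The size depends on figures the documents do not give. Under the assumed 70% bilateral share, 50% eye rate and ρ of 0.3 to 0.9, the all-eyes patient proportion lies about 2 to 12 points below the per-eye figure, and the any-eye proportion lies about 2 to 12 points above it.

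The interval point is conditional. If the synopsis interval is applied as an ordinary binomial interval on pooled eyes, and a child's two eyes correlate positively, the standard error is understated by a factor of 1.10 to 1.38 over the ranges assumed. At zero correlation it is not understated.

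This is a minor point on a descriptive secondary endpoint. The primary endpoint, the futility rules and the success criterion use one outcome per patient and are untouched.

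**What to change.** Use a patient denominator in protocol Table JAHW.12 and SAP Tables JAHW.7.1 and JAHW.7.2, in one of two ways:

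- make separate rows for the more and the less severely affected eye mandatory, with a stated convention for equal baseline grades; or
- define an explicit patient-level two-eye rule. The bilateral-responder endpoint in the same SAP tables already works this way. An all-affected-eyes rule is stricter than the per-eye rate, so it is a choice of endpoint and should be recorded as one.

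Then align the rest with that unit. State how NRI treats a missed visit and a single ungraded eye. Put one eye per patient in each time-to-inactive-disease curve, and correct the method cell so that it names inactive disease. State whether the synopsis 95% interval applies to this endpoint and by which method. If a pooled per-eye rate is also shown, give it an interval clustered by patient, for example from GEE or a bootstrap that resamples patients.

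The cost is rewording in three tables, one re-derived variable and somewhat wider intervals where intervals are shown. No new data are needed.
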